Although studies have shown that some disease management programs may improve patient outcomes in HF, the effect and complexity of disease management programs are highly heterogeneous. Some interventions did not improve patient outcomes, including an intensive model that involved close follow-up by their primary care provider, beginning before discharge and continuing for six months. These findings call for the need of additional models that could potentially account for both efficacy and efficiency, such as SMAs in HF. Our previous successes in SMAs for diabetes, and those of others, suggest that this approach to be an ideal setting to empower patients with HF self-care skills and induce change in self-care behaviors in HF in addition to medication management and disease monitoring to improve their symptoms and health status. However, effectiveness of SMAs in HF management is unknown, and unlike patients with diabetes, a mostly asymptomatic disease in its initial stages, HF patients are vulnerable, especially after hospitalization, with a constant risk of further decline in health status or death. Indeed the national VHA data showed that ~20% of these patients are readmitted within 30 days of their discharge.

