#### **5. HF-SMA at Providence VA Hospital:** The Providence VA instituted multi-disciplinary HF-SMA in 2011.

Patients are referred from inpatient and outpatient setting by their physicians. [name] oversees the HF-SMA in case of difficult patient scenarios. In preparation for this proposal, we abstracted data on 70 patients referred to this program: Mean age:  $75\pm12$  years, Caucasian (93%), 99% male, NYHA class 3 or 4 at baseline visit (66%), mean left ventricular ejection fraction of 42%, and 50% of patients takes  $>10$  prescribed medications. There was a mean of  $41\pm64$  days delay from hospital discharge to attendance of HF SMA. For care coordination, referral into telehealth occurred in 22% and for home care was 4%. Medication changes and dose titration occurred in 62% of patients. Preliminary results showed a 30-day readmission rate of 6% and a 180-day readmission rate of 25% for all patients enrolled in HF SMA. In contrast, data from the VA Inpatient Evaluation Center showed a HF readmission rate for Providence VA at 22% for 2013 and pilot data from a national sample of discharged HF patients ejection fraction  $<40\%$  showed a 180-day readmission rate of 40%, suggesting a possible reduction in rehospitalization rate by HF-SMAs.

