## **C. STUDY DESIGN OR APPROACH**

**1. Overview** This will be an open-label multi-center randomized-controlled trial of parallel design, to study the effectiveness of HF SMA in improving the health status (Aim 1), hospitalization or mortality (Aim 2) of patients discharged from a HF hospitalization. In addition, we will study intermediate outcomes such as process measures of HF-self-care and a biological measure of clinical status (BNP levels) (Aim 3). Finally, we will conduct fidelity assessments and a pre-implementation evaluation through interviews with patients (and caregivers if available and willing) to determine satisfaction and possibilities of refinement of the HF SMA, and physician stakeholders to assess for potential barriers of implementation. We will enroll patients within 12 weeks of discharge from a HF admission and/or IV diuretic therapy, who will be randomized to receive either HF-SMA versus usual care. The conduct of the clinical trial will follow the suggested best practices in the conduct of randomized trials as published in the British Medical Journal. The study duration will be 180 days from the time of randomization. Both quantitative and qualitative methods will be utilized to assess the outcomes of this intervention. The HF-SMA will consist of four sessions of 2-hour duration that occur every other week for 8 weeks or based on the clinics' appointment availability.

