**5. Randomization and retention:** Once enrolled, patients will be randomly assigned on a 1:1 ratio to intervention or placebo arms using a stratified block randomization method with block sizes of 4 in each site to ensure balance of the stratified variables. Stratification will be based on the study site and the presence or not of: a) co-intervention (enrollment to HF clinic, support group or education), b) ≤2 hospitalizations in the last 6 months, and c) left ventricular ejection fraction <40%. Randomization will be done by the call-in method to a central computer administered by the study coordinator at Providence VAMC, the coordinating site. To ensure subject safety and continuous engagement in study procedures, patients will be called by phone by study staff on a monthly basis following randomization to answer any questions that may arise, ask for participation in HF programs and doctor's visits, ER visits, document adverse events and maintain study engagement. Patients in the control arm will be invited to participate in HF-SMAs at the end of the study, to honor patient's preferences.

Our preliminary data showed that our recruitment in prior SMA research has been successful, ~50-60% of those screened and eligible agreed to enroll in SMAs; and then about 90% of those enrolled finished the study. Reasons for drop out are: geographic mobility, change in work schedule, incarceration, and homelessness. Yet, we have been able to maintain a good retention rate, through a combination of excellent relationships with participants, and a perceived value of the study to clients.

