Sample Size and Power Considerations: The overall study sample will be 375 (225 patients from Phoenix VAMC and 150 patients from Providence VAMC). Statistical power for the aims 1 and 2 is estimated given these are the most relevant and the most restrictive in terms of power estimations. Under a conservative dropout rate of 15% for 180 days of follow-up for the main outcomes (Aims 1 and 2), we estimate the power with an effective sample size of 316 (15% less than the total sample) and a 2-sided significance level of 0.05 using nQUERY Advisor 7.0®. For aim 1, we assess the power to detect a clinically significant change in KCCQ of 5 points, assuming a baseline score of 63 (our preliminary studies), with a common standard deviation of 15 for the study arms, using a 2-sample t-test. For aim 2, we assess the power to detect a relevant decrease in rehospitalization or death risk of 25-30% at 180 days using a Cox Proportional Hazards model. Based on our preliminary data of 20,000 Veterans with ejection fraction <40% hospitalized with HF, their rehospitalization rates at 6 months is ~40%. Assuming similar event rates for rehospitalization or death, as shown in Table 2, we have good power to detect the proposed outcomes at very conservative estimates of effective sample size (n=158 in each arm, which is 85% of the total proposed recruitment target). Repeated measures at 90 and 180 days are also likely to add to the statistical power in Aim 1 to detect differences at the subgroup levels.

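### The 40% planning rate for hospitalization or death comes from a different population, clock and endpoint than the trial's, and Aim 2 power should be shown over a range of rates

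*Combined protocol and SAP*

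**What the plan says.** Section 9 (Quantitative Analytic Plan), under Sample Size and Power Considerations, takes its Aim 2 rate from one source: "Based on our preliminary data of 20,000 Veterans with ejection fraction <40% hospitalized with HF, their rehospitalization rates at 6 months is ~40" percent. It then assumes a similar rate for rehospitalization or death. Preliminary Work, item 5, describes what appears to be the same figure, with the same citation, as a 180-day readmission rate in discharged patients with EF below 40%.

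The trial differs on three counts.

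- **Entry.** The Overview states: "We will enroll patients within 12 weeks of discharge from a HF admission and/or IV diuretic therapy". Section 2 (Population) has no EF criterion. EF enters only as a stratifier in section 5, "left ventricular ejection fraction <40"%, and as a subgroup in section 9.
- **Clock.** Sections 1, 8 and 9 count events for 180 days from randomization.
- **Endpoint.** Aim 2 is a composite of hospitalization or death.

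The plan also gives early rates. Nationally, about "20% of these patients are readmitted within 30 days of their discharge" (Background). Phoenix reports 25% at 30 days (Preliminary Work, item 6). Item 5 says Providence patients often put off their appointment to 3–4 weeks, and gives this as a reason for the 12-week window.

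Table 2 states Aim 2 power of 0.75, 0.80, 0.85 and 0.90 at hazard ratios of 0.74, 0.73, 0.71 and 0.69.

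**The concern.** Readmission risk after a heart failure discharge is concentrated early. A rate counted from discharge includes that period; a rate counted from a later randomization leaves some of it out. The plan deliberately opened the window to allow late starts but kept a from-discharge rate. It also carried a rehospitalization rate over to a composite that includes death, and a reduced-EF rate over to all EF.

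The event rate drives power in a time-to-event comparison. If the 40% does not describe the patients who will be randomized, a null result on hospitalization or death would be judged against power that the plan has not supported. Correcting Table 2 at 40% alone would carry the same mismatch forward.

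**Working it through.** **Inputs.** "The overall study sample will be 375"; "patients will be randomly assigned on a 1:1 ratio"; "2-sided significance level of 0.05"; 158 effective patients per arm (316 in all); control rate 40%. All come from section 9 except the allocation (section 5).

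**Formulas.** With control rate p and hazard ratio HR, expected events d = 158 × [p + 1 − (1 − p)^HR]. Power = Φ(√(d/4) × |ln HR| − 1.96).

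**1. The plan's own figures.** At p = 0.40 and HR 0.73: 0.60^0.73 = 0.689, so d = 158 × (0.40 + 0.311) = 112.4. With |ln 0.73| = 0.3147, power = Φ(5.30 × 0.3147 − 1.96) = Φ(−0.29) = 0.385.

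| HR | Stated power | Power at 40% control rate | Power if d = 316 |
|---|---|---|---|
| 0.74 | 0.75 | 0.36 | 0.76 |
| 0.73 | 0.80 | 0.385 | 0.80 |
| 0.71 | 0.85 | 0.44 | 0.86 |
| 0.69 | 0.90 | 0.495 | 0.91 |

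One-sided alpha, no dropout, 40% as the overall rate, 60% events, the Freedman formula at 40% and a two-proportion test all fail to match. Only 316 events, one for every effective patient, reproduces every row. The Aim 1 column does reproduce (0.76, 0.84, 0.90, 0.945).

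**2. Effect of a later start (illustration).** Assume 40% by day 180, r by day 30 with r = 0.20 or 0.25, constant hazard within each period, and patients event-free at the start.

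- Daily hazard, days 0–30: −ln(1 − r)/30 = 0.00744 or 0.00959.
- Daily hazard after day 30: ln((1 − r)/0.60)/150 = 0.00192 or 0.00149.
- Start at day 14 (16 early days, 164 later days): 1 − exp(−0.434) = 35%, or 1 − exp(−0.397) = 33%.
- Start at day 30 or later: 1 − exp(−180 × 0.00192) = 29%, or 1 − exp(−180 × 0.00149) = 23.5%.

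**3. Adding deaths (upper bound).** Background gives mortality of 6% at 30 days and 30% at one year. Treat every death as an extra first event.

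- Daily death hazard after day 30: ln(0.94/0.70)/335 = 0.00088. Before day 30: −ln(0.94)/30 = 0.00206.
- Start at day 30 or later: 35% (r = 0.25) to 40% (r = 0.20).
- Start at day 14: extra cumulative hazard 16 × 0.00206 + 164 × 0.00088 = 0.177, giving 44% to 46%.

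These are ceilings, because some deaths follow a readmission already counted and hospice patients are excluded.

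**4. Power at HR 0.73 over a range of control rates.**

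| Control rate | Expected events | Power |
|---|---|---|
| 25% | 69 | 0.26 |
| 30% | 84 | 0.30 |
| 35% | 98 | 0.34 |
| 40% | 112 | 0.385 |
| 50% | 142 | 0.47 |

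**The case against.** The strongest reply is that the net error is not established. Most of its parts stand.

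- **Past the early peak.** A reader might infer that randomized patients are beyond the early peak and that this peak makes up about half of the 40%. The documents do not support either. The 20–25% early figures and the 40% come from different cohorts, the 22% for Providence has no stated window, and no 30-day share is given for the EF <40% cohort. There is no event-free entry criterion: a heart failure readmission gives a new discharge date and a fresh window. Some patients may also enrol before day 30. The pilot mean of 41 days (SD 64) is time to clinic attendance, not to randomization.
- **Deaths.** Adding them can cancel the effect of the later start. For an early start the ceiling exceeds 40%.
- **EF mix.** A reader might infer that including EF ≥40% lowers the rate. The documents give no rate for those patients. Pilot mean EF was 42% at Providence but 35% at Phoenix, which is to supply 225 of the 375.
- **Conservatism.** A reader might take the plan's phrase about very conservative estimates as a claim about the event rate. It describes the effective sample size and needs no change on this ground.
- **Larger error elsewhere.** Table 2 does not reproduce even at 40%, so restating the rate alone would not correct it, and Aim 2 is secondary. That is right, and is why both should be handled in one correction.

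What remains is that the 40% is the only planning rate, it differs from the trial in population, clock and endpoint, and nothing adjusts for this.

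**Conclusion.** The mismatch is documented and unadjusted. The control rate is probably below 40%, but that is not proven. The later clock pulls it down, deaths push it up, and the EF effect is unknown. The illustrative rates rest on combining cohorts, on constant hazards within periods, and on patients being event-free at the start.

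The conclusion on power does not depend on settling the direction. At HR 0.73 with 158 per arm it is about 0.26 to 0.385 for control rates of 25–40%, and 0.47 even at 50%, against the stated 0.80. It would be wrong to blame the planning rate for most of that gap: the fall from 0.80 to 0.385 arises at 40% itself, and the rate mismatch adds uncertainty around the lower figure. Aim 1 power is unaffected.

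**What to change.** In Sample Size and Power Considerations, state that the 40% is a rehospitalization-only rate counted from discharge in patients with EF below 40%, and that the trial differs on all three. Replace the Aim 2 column of Table 2 with event-based power at 158 per arm over a range of control rates, such as the 25–50% shown above. Withdraw the statement that power is good for Aim 2.

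Where the sponsor's data allow, narrow the range. Re-cut the discharge cohorts across all EF, start from landmarks after the most recent discharge, restart the clock at each readmission, and count hospitalization or death over the next 180 days. The 20,000-patient cohort is described as EF <40% only, so all-EF rates would need another source. The cohort of more than 100,000 in Background may serve, but its EF and readmission data are not described.

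The text and table changes need no new data, and enrolment stays as planned. The cost is that the stated Aim 2 power becomes less favourable; the re-cut adds analysis work if the data exist.

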## **B. INNOVATION**

The innovations are: 1) a rigorous and well-powered experiment to test the effectiveness of SMAs in HF is much needed to fill the knowledge gap on HF-SMA and its effects on outcomes meaningful to the patient, the provider and the VHA (aims 1-4). Given the 2-site design (East and West regions), we will be able to perform an assessment of *heterogeneity of treatment effects*, if any, and select out system factors (hospital/provider) if any, and patient subgroups that favored SMA intervention, even when the overall trial shows a non-significant result. 2) Our mixed method approach and the planned pre-implementation assessment will help understand potential mechanisms of benefit, if any, thereby, streamline and refine the intervention in the next iteration, in preparation for broader implementation. 3) Given the poor health status of patients with HF, traditional treatment settings required intensive physician involvement to show clinical efficacy, especially after hospitalization. Therefore, our study will address whether the addition of non-physician health professionals, via SMA approach, may improve patient outcomes. 4) If proven effective, our intervention will add another care delivery model to treat HF and possibly other complex chronic diseases alike that have frequent exacerbations. **The importance of developing a new and robust intervention to improve patient outcomes in HF cannot be overemphasized, especially given recent literature that showed not all interventions in HF work as planned.** Examples of such ineffective interventions are regular follow-up calls after discharge or close follow-up by primary care, which did not improve patient outcomes despite better patient satisfaction. Because experimental interventions can have a neutral or even negative effect on outcomes, we have chosen a neutral comparator (usual care) rather than an active comparator.

Thus, *this randomized-controlled trial to test the effectiveness of HF-SMA in improving patient outcomes after hospital discharge is timely and critically needed to create an innovative approach to HF management, and support patients with symptomatic HF. Currently, patients with HF may have limited options in traditional care models which strain system resources and fail to comprehensively address patient needs.*

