**Table 2. Power / Effect Size Calculations at 180 days Intervention vs. Usual Care**

Aim 1: Difference in KCCQ		Aim 2. Risk of Rehospitalization or death	
Difference in mean KCCQ	Power	Hazard Ratio	Power
4.5	.76	0.74	0.75
5	.84	0.73	0.80
5.5	.90	0.71	0.85
6	.95	0.69	0.90

10. Qualitative Analysis: All interviews will be audio recorded and fully transcribed. We will use qualitative data analysis software, NVivo (QSR International, Melbourne, Australia) to organize, code and retrieve qualitative data, summarize linkages across themes and maintain analytic notes of the coders. Transcripts and field notes from observations of the intervention (not video recorded for privacy reasons) to monitor fidelity will be entered in the database and line- by-line open and thematic coding will be conducted to identify key themes/factors. Qualitative data analysis will be conducted through an iterative process in which members of the research team engage in both data collection and analyses throughout the study. This allows for researchers to refine

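### Table 2's Aim 2 power of 0.75–0.90 matches about 316 events (every analysed patient); at the plan's own 40% event rate it is about 0.36–0.49.

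*Combined protocol and SAP*

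**What the plan says.** The power paragraph of Section 9 (Quantitative Analytic Plan) sets the inputs. On recruitment: "The overall study sample will be 375". After 15% dropout the calculation uses an "effective sample size of 316 (15% less than the total sample", which is "n=158 in each arm, which is 85% of the total proposed recruitment target", with a "2-sided significance level of 0.05 using nQUERY Advisor 7.0". Aim 2 is to be tested with a Cox model against a 25–30% reduction in risk at 180 days.

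The event rate comes from preliminary data on Veterans with ejection fraction below 40% hospitalized with heart failure: "their rehospitalization rates at 6 months is ~40" per cent. The paragraph carries that rate over to the composite and concludes: "Assuming similar event rates for rehospitalization or death, as shown in Table 2, we have good power to detect the proposed outcomes".

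Table 2, titled "Power / Effect Size Calculations at 180 days Intervention vs. Usual Care", lists for Aim 2:

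- HR 0.74: power 0.75
- HR 0.73: power 0.80
- HR 0.71: power 0.85
- HR 0.69: power 0.90

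The Aim 2 analysis text in the same section censors patients who are event-free at 180 days. No expected number of events is given. Section B (Innovation) describes the trial as "a rigorous and well-powered experiment to test the effectiveness of SMAs in HF".

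**The concern.** Power to detect a hazard ratio is set by the number of events; patients censored at 180 days add almost nothing to it. With an event rate of about 40%, most of the 316 analysed patients will be censored, yet Table 2 shows power that would require nearly all of them to have an event.

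Aim 2 is listed under Secondary Aims, but the power paragraph groups it with Aim 1 as a main outcome, powers it formally and calls the power good. Hospitalization and death are also part of the project's stated primary goal. A reader who trusts Table 2 would take a non-significant Aim 2 result as fairly strong evidence against a hazard ratio of about 0.7. If the true power is below one half, such a result says little.

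**Working it through.** **Inputs.** Two-sided alpha 0.05, 158 analysed per arm (316 in total), and a 6-month event rate of about 40%, all from the power paragraph. 1:1 allocation from Section 5. Hazard ratios and stated power from Table 2.

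**Formula.** Schoenfeld approximation with equal allocation and D events: power = Φ(√(D/4) × |ln HR| − 1.960).

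**Step 1: reproduce Table 2.** Put D = 316, so √(316/4) = 8.888.

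| HR | \|ln HR\| | 8.888 × \|ln HR\| | Power, D = 316 | Table 2 |
|---|---|---|---|---|
| 0.74 | 0.301 | 2.676 | 0.763 | 0.75 |
| 0.73 | 0.315 | 2.797 | 0.799 | 0.80 |
| 0.71 | 0.342 | 3.044 | 0.861 | 0.85 |
| 0.69 | 0.371 | 3.298 | 0.910 | 0.90 |

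Freedman's form with 316 events gives 0.757, 0.792, 0.854 and 0.903. Both match every row within two points. In reverse, the events needed for the stated power are 307, 317, 307 and 306, or 97–100% of the 316 patients. For HR 0.73 at 80%: 4 × (1.960 + 0.842)² / (ln 0.73)² = 317.

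**Step 2: apply the plan's 40%.** Take 40% as the usual-care risk, since it comes from patients outside the intervention. Under proportional hazards the intervention risk is 1 − 0.60^HR, and D = 158 × 0.40 + 158 × (1 − 0.60^HR).

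| HR | Intervention risk | Events D | √(D/4) × \|ln HR\| | Power | Table 2 |
|---|---|---|---|---|---|
| 0.74 | 31.5% | 112.9 | 1.600 | 0.36 | 0.75 |
| 0.73 | 31.1% | 112.4 | 1.668 | 0.39 | 0.80 |
| 0.71 | 30.4% | 111.3 | 1.806 | 0.44 | 0.85 |
| 0.69 | 29.7% | 110.1 | 1.947 | 0.49 | 0.90 |

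Freedman gives 0.36, 0.38, 0.43 and 0.49. A log-rank simulation (4,000 runs per hazard ratio, exponential times, censoring at 180 days) gives 0.36, 0.38, 0.43 and 0.50.

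**Step 3: what the design can detect.** Solving for 80% power with D as in Step 2 gives HR 0.58, with about 104 events. HR 0.73 at 80% needs 317 events. The average risk there is (0.400 + 0.311)/2 = 0.356, so 317/0.356 ≈ 890 analysed patients, or about 890/0.85 ≈ 1,050 recruited.

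**Step 4: more generous readings**, over HR 0.74 to 0.69:

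- 40% as the overall rate (126 events): 0.39–0.55
- 40% in usual care, all 375 patients, no dropout: 0.41–0.56
- 40% of all 375 as events (150 events): 0.45–0.62
- one-sided test, 40% overall: 0.52–0.67
- two-proportion test with the HR read as a risk ratio: 0.49–0.65
- 40% read as event-free, so 60% usual-care events: 0.51–0.67
- 80% usual-care events: 0.64–0.81

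Each falls short of Table 2 on every row. If the 25–30% reduction means risk falling from 40% to 30% or 28%, the hazard ratios are ln 0.70/ln 0.60 = 0.70 and ln 0.72/ln 0.60 = 0.64, with power 0.47 and 0.63.

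**Step 5: other event rates (assumed usual-care values).** Power from HR 0.74 to 0.69 is 0.24–0.33 at 25%, 0.28–0.39 at 30%, 0.44–0.59 at 50% and 0.51–0.67 at 60%.

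**Step 6: Aim 1 column.** With SD 15 and 158 per arm, a two-sample comparison gives 0.76, 0.84, 0.90 and 0.945 for differences of 4.5, 5, 5.5 and 6. This agrees with Table 2, so the sample size and alpha are being read correctly and the error is confined to Aim 2.

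**The case against.** **The cause is inferred.** The plan does not say that 316 was entered as the event count. A different slip gives identical figures: a Cox calculation with covariate standard deviation 1 instead of 0.5, and 79 events (25% of 316). This stands as a limit on explaining how the table arose. It does not help the table, because that input would also be wrong for a 1:1 comparison, and the stated power cannot be obtained from a 40% event rate by any reading tried.

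**Aim 2 is secondary.** The primary outcome is KCCQ, its power is right, and 375 equals the recruitment plan (50 + 75 per year over three years). That is correct and limits the damage: the primary inference is untouched. But the plan itself powers Aim 2 and draws a conclusion from that calculation, and the conclusion is wrong.

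**The event rate could be higher than 40%.** The source figure is rehospitalization alone, the endpoint adds death, and the Background reports 30% one-year mortality after admission. It could equally be lower: the source cohort had ejection fraction below 40%, whereas the trial has no such limit, enrols up to 12 weeks after discharge and counts events from randomization. The Providence pilot saw 25% readmission at 180 days among SMA patients. Both directions belong in a sensitivity table. Even 60% gives only 0.54 at HR 0.73.

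**Conclusion.** The concern holds. Table 2's Aim 2 power is inconsistent with the event rate given in the paragraph that introduces it. With 158 analysed per arm, two-sided 0.05, proportional hazards and a 40% usual-care risk, power is about 0.36, 0.39, 0.44 and 0.49 where the plan states 0.75, 0.80, 0.85 and 0.90. It is roughly half the stated value in each row. At HR 0.73 the chance of missing the effect is about 0.61, against a stated 0.20.

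Reading 40% as the overall rate moves the range to 0.39–0.55; usual-care rates from 25% to 50% span 0.24 to 0.59. None of these supports the good-power statement. That all 316 patients were counted as events is the simplest explanation of the table, but the conclusion does not depend on it.

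**What to change.** 1. Replace the Aim 2 columns of Table 2 with event-based figures, stating the method and the expected events: at a 40% usual-care rate, about 113, 112, 111 and 110 events and power 0.36, 0.39, 0.44 and 0.49 for HR 0.74, 0.73, 0.71 and 0.69. Give the hazard ratio detectable at 80% power as about 0.58 (about 104 events).
2. Add rows for assumed usual-care rates either side of 40%, for example 25%, 30% and 50%, and say that the 40% comes from a different population and from rehospitalization alone.
3. State whether the 25–30% reduction is in risk or in hazard.
4. Remove the claim of good power for Aim 2, and limit the well-powered description in Section B to the primary outcome.
5. State that Aim 2 will be reported as a hazard ratio with its 95% confidence interval, and that a non-significant result will not be taken as evidence of no effect.

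The cost is a rewrite of one paragraph, half of one table and a phrase in Section B. No patients, visits or procedures change. The price is that the plan must show a less favourable figure for Aim 2.
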